7.2 Measures taken to avoid bias

All necessary steps will be taken to reduce the risk of bias. Detection bias will be minimised by blinding of laboratory staff analysing cytokines, biomarkers and inflammatory processes. Specifically, urine, serum and sputum samples obtained exclusively for the trial will be identified only by a trial acronym, patients' study ID, initials and date of birth and the time at which the sample was taken, ensuring that laboratory staff performing analyses are blinded. Detection bias for the clinical outcomes will also be minimised by the use of objective outcome criteria. Other samples, that are also obtained as part of routine care will be analysed routinely in NHS laboratories by personnel who are unaware that the participant is in a trial. Clinical decision about patient care will be made by clinical staff on the basis of existing institutional protocols and will not be affected by enrolment in the study.

7.3 Plan of analysis

A statistical analysis plan will be drafted prior to analysis. Normally distributed data will be presented as means (standard deviation). Non normally distributed data will be presented as geometric means (95% confidence intervals). Dichotomous data will be presented as percentages. This data will be used to quantify the number of patients required to design a further prospective observational analysis.

7.4 Criteria for stopping the study early

The study may be terminated early if the results of another study supersedes the necessity for completion of this study.

8. Study Management

The study will be managed by the Cardiac Surgery Clinical Trials Team (CSCTT) at the University of Leicester. The CSCTT will prepare trial documentation and data collection forms, register patients and carry out trial procedures; the CSCTT will also develop and maintain the study database, check data quality as the trial progresses, and carry out trial analyses in collaboration the statistician.

8.1 Day-to-day management

The trial will be managed by a Clinical Trial Manager, supported by a Clinical Trial Coordinator from the Cardiac Surgery Clinical Trials Team at the University of Leicester. An authorised ECMO fellow/coordinator will be responsible for managing the trial on a day-to-day basis. They will be responsible for identifying potential trial participants, seeking informed patient consent, liaising with blood and laboratory services, collecting trial data and ensuring the trial protocol is adhered to.

8.2 Trial steering committee and data safety & monitoring committee

The trial will be monitored by the Cardiovascular Surgery Research Group Steering Committee. As this is an observational study, no Data Monitoring and Safety Committee (DMSC) will be convened.

The Trial Steering Committee will provide overall supervision of the trial and ensure that the local, national and international research framework is adhered to. The Trial Steering Committee will agree trial amendments, as necessary, and provide relevant guidance on study design and conduct to participating investigators. Membership includes members of the Trial executive, principal investigators, independent experts, a service user representative and a representative of the study Sponsor.

9. Safety Reporting

9.1 *Definitions*

As defined by the ICH Guidelines for Good Clinical Practice (CPMP/ICH/135/95) the following definitions will be used:

Adverse Event

Any untoward medical occurrence in a patient or clinical trial subject, who has been administered a clinical intervention, procedure, treatment or medicinal product and which does not necessarily have a causal relationship with this medical intervention. An adverse event can therefore be any unfavourable and unintended sign (including an abnormal laboratory finding), symptom or disease temporally associated with the intervention, whether or not related to the medical intervention.

Serious Adverse Event

Any untoward medical occurrence, which

- results in death
- is life threatening
- requires inpatient hospitalisation or prolongation of existing hospitalisation
- results in persistent or significant disability or incapacity
- consist of a congenital anomaly or birth defect.
- other situations, such as significant medical events, which may not be immediately life threatening or result in death or hospitalisation, but which may jeopardise the subject or may require intervention to prevent one of the other serious outcomes listed in the definition above, should also be considered.

9.2 *Adverse event reporting*

Adverse events will be recorded and reported in accordance with the University of Leicester's and University Hospitals Leicester NHS Trust's policies for reporting Research Related Adverse Events.

In intensive care management and especially in ECMO practice, adverse events are not unexpected and are not infrequent. The research team will only notify deaths and 'unexpected' non-fatal SAEs to the Trial Sponsor (University of Leicester Research Support Office). Unexpected events are those not listed in the trial protocol or on the case report forms. The sponsor will inform the research team which SAEs should be reported to the REC.

9.3 *Expected adverse events*

The following adverse events are 'expected':

Cardiovascular:

- Cardiac arrest
- Myocardial stunning
- Cardiac arrhythmias and arrhythmias requiring temporary or permanent pacing
- Myocardial infarction including:
 - New Q's in 2 contiguous leads
 - Raised Troponin I >0.5µg/l
 - New ST depression >2mm in 2 leads
- Cardiac tamponade
- Pericardial effusion
- Perforation of heart or vessels
- Cardiopulmonary resuscitation including cardiac defibrillation/DC shock
- Chest opening
- External/internal cardiac massage
- Low cardiac output
- Haemodynamic support, including use of:
 - Any inotropes
 - Pulmonary artery catheter
 - Any vasodilators

Pulmonary:

- Prolonged invasive ventilation
- Tracheostomy
- Bronchomalacia
- Tracheomalacia
- Subglottic stenosis
- Initiation of mask continuous positive airway pressure ventilation after weaning from ventilation
- Acute Respiratory Distress Syndrome
- Pneumothorax or effusion requiring drainage

Thromboembolic complications, including:

- Deep vein thrombosis
- Pulmonary embolism
- Clotting of the ECMO circuit
- Stroke
- Arterial thrombosis
- Limb ischemia

Hemorrhagic complications, including:

- Disseminated intravascular coagulation
- Haemothorax
- Cannulation site bleeding
- Gastrointestinal bleeding
- Brain haemorrhage
- Haemolysis
- Airways bleeding

Renal complications, including:

- Acute kidney injury

- Haemofiltration/dialysis

Infective complications, including:

- Sepsis (defined as antibiotic treatment for suspected infection, and the presence of SIRS¹ within 24 hours prior to start of antibiotic treatment) - SIRS will be defined as ≥ 2 of the following conditions: temperature $>38^{\circ}\text{C}$ or $<36^{\circ}\text{C}$; heart rate >90 beats/minute; respiratory rate >20 breaths/min or $\text{PaCO}_2 < 32$ mm Hg or < 4.3 kPa; white cells count $>12,000/\text{mm}^3$ or $<4,000/\text{mm}^3$.
- Septic shock
- Wound infection
- Respiratory infection
- Ventilator associated pneumonia
- Urinary tract infection
- Catheter related bloodstream infection

GI complications, including:

[figure not shown]
- Pancreatitis (amylase $>1500\text{iu}$)
- NEC (necrotizing enterocolitis)
- Other (e.g. laparotomy)

Neurological complications

[figure not shown]
- Irreversible neurological deficit
- Seizures
- Peripheral nerve damage

Figure 3: Serious adverse event reporting flow chart

(a) Unexpected serious adverse events – i.e. those not listed in study protocol

(b) Expected serious adverse events – i.e. those listed in study protocol

9.4 *Period for recording adverse events*

Data on adverse events will be collected from ECMO commencement to UHL discharge.

9.5 *Methods of recording and assessing adverse events*

Prior to study registration, a detailed medical history and physical examination, including laboratory tests, will be taken for baseline reference. At all subsequent days of hospital admission and during the follow up, the occurrence of AEs will be recorded in the appropriate section of the CRF. Among these, all SAEs must also be recorded in the SAE report form and will be notified to the Trial Sponsor (University of Leicester Research Support Office) in case of death or 'unexpected' non-fatal SAEs.

The following aspects of AEs will be captured in the CRF:

- Description of event in medical term
- Date of onset
- Date of recovery, if applicable
- Intensity of the event:
 - Mild: Awareness of event, but easily tolerated
 - Moderate: Discomfort enough to interfere with usual daily activity
 - Severe: Inability to carry out usual daily activity
 - Life-threatening: Life-threatening or disabling
 - Fatal: Death related to the AE
- Causal relationship to the study procedures as assessed by the Investigator. The decisive factor in documentation is the temporal relationship between the AE and study intervention. The following judgements of causality are to be used:
 - Not related: The event is related to an aetiology other than study procedures
 - Remote: The event is unlikely to be related to the study procedures based on existing knowledge and likely to be related to other factors.
 - Possibly: Reasonable possibility that the AE was caused by the study procedures and there is a plausible mechanism of action, but there may also be an alternative aetiology such as the participant's clinical status or underlying disease.
 - Definite: There is an association between the event and the administration of study procedures, a plausible mechanism for the event to be related to the study product and causes other than study product have been ruled out.
- Action taken: None, Concomitant medication or therapy or other

10. Ethical Considerations

10.1 *Review by a NHS Research Ethics Committee*

Ethics review of the protocol for the trial and other trial related essential documents (e.g. patient information leaflet, consent form) will be carried out by a UK NHS Research Ethics Committee (REC). Any amendments to these documents, after a favourable opinion from the REC has been given, will be submitted to the REC for approval prior to implementation.

10.2 *Risks and anticipated benefits*

The response of neonates to ECMO is still poorly understood in terms of inflammatory signalling and interaction between the body and the machine. However, the haematological response to the circuit in low weight patients is considered to play an important role in the recovery process and in morbidity and mortality. There is a clear need for the development of novel interventions that reduce the severity of inflammatory organ injury during ECMO support. This study may lead to further research that will help future ECMO patients however there are no direct benefits to the recruited patients from taking part.

As this is a non-interventional study, the potential risks from participating in the study are those risks associated with the trial procedures. Specifically the withdrawal of significant volumes of blood from children subject to an ECMO where circulating volume is smaller than in adults is our chief concern.

To minimise this risk, we have taken steps to reduce the volume of blood removed from the children during and after the extracorporeal support. The volumes and tests to be undertaken are determined by patients weight and the minimum volumes of blood required to complete the assays. The detailed consideration of these factors is described in detail in Section 6.1 and Table 2. Our experience with a previous study in paediatric cardiac surgery [The p-MiVAKI study (63)], has shown that these volumes

are safe. We therefore do not anticipate that any child will be exposed to increased risk by participation in the study.

No further invasive procedure will be carried out only for research purposes. Since the airway suctioning is performed routinely for clinical purpose and in the interest of the patient, no ethical issues can be raised.

In summary, the study investigations have a low risk profile, but there are no direct benefits to be gained from trial participation other than helping the researchers in gaining a better understanding about the inflammatory processes that are involved in neonatal ECMO.

10.3 Informing potential study participants of possible benefits and known risks

Information about benefits and risks of participation will be described in a Patient Information Leaflet. This information sheet will be part of our application for research ethics approval to the REC.

10.4 Obtaining informed consent from participants

All participants will be required to give written informed consent to participate in the study. The consent process, including the information about the trial given to patients in advance of recruitment, has been described previously. Members of the clinical research team will be responsible for the consent process.

11. Research Governance

This clinical trial will be sponsored by the University of Leicester and will be conducted in accordance with:

- International Conference for Harmonisation of Good Clinical Practice (ICH GCP) guidelines
- Research Governance Framework for Health and Social Care, the European Union Directive 2001/20/EC on clinical trials
- Data Protection Act 1998.
- Human Tissue Act 2004
- Protection of Children Act, 1999

11.1 Sponsor approval

Any amendments to the trial documents must be approved by the sponsor prior to submission to the REC and/or implementation.

11.2 NHS approval

Approval from University Hospitals Leicester NHS Trust will be obtained prior to the start of the trial.

Any amendments to the trial documents approved the REC will be submitted to the Trust for information or approval as required.

11.3 Investigators' responsibilities

The investigators will be required to ensure that the local research approvals have been obtained and that any contractual agreements required have been signed off by all parties before recruiting any participants. Investigators will be required to ensure compliance to the protocol and study manual and with completion of the CRFs. Investigators will be required to allow access to study documentation or source data on request for monitoring visits and audits performed by the Sponsor or any regulatory authorities.

Investigators will be required to read, acknowledge and inform their trial team of any amendments to the trial documents approved by the REC that they receive and ensure that the changes are complied with.

11.4 *Monitoring by sponsor*

The study will be monitored and audited in accordance with the University of Leicester policy which is consistent with the Research Governance Framework. All trial related documents will be made available on request for monitoring and audit by University of Leicester, the relevant REC and for inspection by the Human Tissue Authority (HTA) or other licensing bodies.

11.5 *Indemnity*

University of Leicester insurance will cover potential legal liability of the sponsor from harm to participants arising from the management and design of the research. NHS indemnity will cover potential legal liability of investigators/collaborators arising from harm to participants in the conduct of the research.

11.6 *Clinical Trial Authorisation*

This is not a randomised trial of an Investigational Medicinal Product and as such a Clinical Trial Authorisation from the MHRA is not required.

12. Data Protection and Patient Confidentiality

12.1 *Data protection*

Data will be collected and retained in accordance with the Data Protection Act 1998.

12.2 *Data handling, storage and sharing*

12.2.1 Data handling

Data will be entered onto a purpose designed database and data validation and cleaning will be carried out throughout the trial. Standard operating procedures (SOPs) for database use, data validation and data cleaning will be available and regularly maintained.

12.2.2 Data storage

All study documentation will be retained in a secure location during the conduct of the study. All the personal data will be stored for 3 years and all the anonymised data will be stored for 15 years after the end of the study, when all paper records will be destroyed by confidential means. In compliance with the MRC Policy on Data Preservation, the pseudonymised dataset, a separate secure electronic 'key' with a unique patient identifier, and relevant 'meta'-data about the trial will be retained in

electronic form indefinitely because of the potential for the raw data to be used subsequently for secondary research.

KDIGO	The International Society of Nephrology: Kidney Diseases Improving Global Outcomes (KDIGO) definition of acute kidney injury (AKI)
MAS	Meconium aspiration syndrome
MABP	Mean arterial blood pressure
MCP	Monocyte chemoattractant protein
MI	Myocardial infarction
MP	Microparticles
MV	Microvesicles
NGAL	Neutrophil gelatinase associated lipocalin
NO	Nitric oxide
pCO ₂	Partial pressure of carbon dioxide
PEEP	Positive End Expiratory Pressure
PICU	Paediatric intensive care unit
PIL	Patient information leaflet
PPHN	Persistent pulmonary hypertension of the newborn
RDS	Respiratory distress syndrome
SaO ₂	Oxygen saturation
SIRS	^{Sy} stemic inflammatory response syndrome
SOP	Standard operating procedures
TNF-α	Tumour necrosis factor – alpha

1. Introduction

The Mi-ECMO study is a pilot feasibility study to consider the relationship between markers of red cell damage, inflammation and the recovery process of newborns requiring Extra-Corporeal Membrane Oxygenation (ECMO) for Persistent Pulmonary Hypertension of the Newborn (PPHN).

This Statistical Analysis Plan (SAP) describes the analysis and reporting for the Mi-ECMO study. It outlines the planned analysis to be performed on the data. Exploratory post-hoc or unplanned analysis not necessarily identified in this SAP may be performed as required.

1.1 Aims and Objectives

Hypothesis

The primary hypothesis is that damage to red blood cells by the exposure to the ECMO circuit will result in inflammatory responses that mitigate against successful weaning from ECMO for PPHN.

The secondary hypothesis are:

1. Damage to red cells will result in platelet, leukocyte and endothelial activation.
2. Markers of platelet, endothelial and leukocyte activation are indicators of lung inflammation and injury severity and hence lung recovery.
3. Markers of platelet, endothelial and leukocyte activation are indicators of kidney injury severity and hence acute kidney injury.
4. Granulocyte and platelets activation are secondary to rising redox potential and the levels of activation will correlate with longer intubation times and more severe organ injury.
5. Markers of platelet, endothelial and leukocyte activation have diagnostic and prognostic utility for the prediction of key clinical events including delayed time to recovery, acute kidney injury in paediatric patients undergoing ECMO for PPHN.

Objectives

The Mi-ECMO study was designed to be a feasibility study, and the results will be used to assist with the design of a prospective observational study that will test the above hypotheses. The objectives of the study are:

1. To determine the recruitment rates and patient flows for 24 patients recruited for the feasibility study.
2. To determine the withdrawal rate and the completeness of follow-up and data collection in a paediatric population at high risk for death and major morbidity.
3. To collect data on primary and secondary outcomes of interest, which may be used to model the sample sizes and outcomes in future study.
4. To collect data on perception of family members, whose children participate in the study, as to their understanding of the screening and consent process (Appendix 1).

Changes in hypothesis

Due to the lack of ethical approval, this study is not conducting analysis of bronchial aspirates, and measuring markers of oxidative stress and MV levels. The following secondary hypothesis which were stated in the study protocol have not been included in this SAP:

1. The level of oxidative stress will correlate with type shifts in pulmonary macrophages, tissue iron deposition and organ injury.
2. Ability to raise anti-oxidative response, measured by Heme Oxygenase-1 (HMOX 1) expression, will correlate with shorter intubation times and less severe kidney and lung injury.
3. Markers of anti-oxidative response and oxidative stress levels have diagnostic and prognostic utility for the prediction of key clinical events including delayed time to recovery, acute kidney injury in paediatric patients undergoing ECMO for PPHN.

Correspondingly, all related secondary outcomes would not be included in this SAP.

1.2 Study Design

The Mi-ECMO study is a prospective, single-centre observational feasibility study.

1.3 Sample Size

The Mi-ECMO study enrolled 24 patients. There was not a formal power calculation for this feasibility study. The sample size was based on the observations from a similar study, p-MiVAKI which had recruited 24 paediatric patients and was able to demonstrate differences in the primary outcomes, markers of platelets, leukocyte and endothelial activation, between those who did and did not develop AKI, and between those did and did not receive transfusion.

1.4 Study population

The study was conducted at Glenfield Hospital, a regional ECMO centre in the UK, the University Hospitals of Leicester NHS Trust. The Glenfield Hospital is a national paediatric referral centre and provides ECMO support across UK from phone consultation to onsite cannulation and transport on ECMO. This unit performs over 60 neonatal and paediatric ECMO per year, of which at least 40 are expected to be performed for the treatment of PPHN in infants.

Participants of this study were consecutive patients referred to the Glenfield Hospital according to the ECMO referral system who match the following study criteria.

Inclusion Criteria

Participant may enter study if all of the following apply:

1. Patients with a diagnosis of PPHN
2. Patients that require ECMO support as determined by the ECMO team
3. Patients aged less than 30 days
4. Emergency consent obtained within 12 hours from cannulation, and ultimately full consent

Exclusion criteria

Participant may not enter study if any of the following apply:

1. PPHN is caused by a congenital heart pathology
2. ECMO is required for a congenital heart disease
3. Lack of consent

1.5 Schedule of Major Assessments

	Baseline (12h after ECMO start +/- 6 hrs)	Day 1 (24 hrs +/- 12 hrs)	Day 2 (48h +/- 12 hrs)	Day 3 (72h +/- 12 hrs)	24h after decannulation/ prior to ECMO stop for death or withdrawal (+/- 12 hrs)
Eligibility	✓				
Written emergency consent	✓				
Trial Registration	✓				
Clinical outcomes	✓	✓	✓	✓	✓
Serious adverse event monitoring	✓	✓	✓	✓	✓
Bloods: Full blood count	✓	✓	✓	✓	✓
Bloods: Cytokines, total iron, non-transferrin-bound iron	✓	✓	✓	✓	✓
Bloods: Platelets and leukocyte activation	✓	✓	✓	✓	✓
Bloods: MV analysis	✓	✓	✓	✓	✓
Respiratory Sample: ferrocyanide, oxidative stress	✓	✓	✓	✓	✓
Urine sample & volume: NGAL	✓	✓	✓	✓	✓
Questionnaire on perception of family members					✓

2. Endpoints

A list of variables to be evaluated and reported in the statistical analysis is provided in the Appendix.

2.1 Primary outcomes

Markers of cellular activation including platelet, leukocyte and endothelial cell activation in arterial blood at baseline (12 hours after ECMO commencement) and then at 24, 48 and 72 hours post commencement and at weaning (24 hours after decannulation) or immediately prior to ECMO support being stopped in case of death or treatment withdrawal.

Markers of cellular activation include CD41, PAC-1 and CD62P for platelets, CD64 and CD163 for leukocytes, CD14, CD16, and CD41 for platelet-leukocyte aggregates, as well as circulating ICAM and E-selectin for endothelial injury.

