2.3 Target conditions

1. Prolonged ECMO defined as patients remained on ECMO at day 7 (duration of ECMO >168 hours)
2. AKI as defined by the KDIGO stage 1, 2 or 3 using the paediatric AKI definition (Table 1).
3. AKI as defined by the KDIGO stage 1, 2 or 3 using the serum creatinine criteria for the neonatal AKI definition (Table 2).

3. Analysis Sets/Populations

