4.3 Descriptive Analysis

Descriptive analysis will be presented for demographic and baseline characteristics, as well as the primary and secondary outcomes, and targeted conditions described in Section 2. For categorical variables, numbers and percentages will be presented. For continuous variables, mean and standard deviation or median with lower and upper quartiles, as appropriate, will be presented.

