4.4 Statistical Methods

Mixed effects model with patient as random effect will be used to analyse outcomes measured at multiple time points. Logarithm transformation will be considered for skewed variables. Linear graphs showing the variation of the mean measurements over time will be displayed.

Exploratory analysis are to be carried out using mixed effects models to examine serial makers of cellular activation and their relationship with:

- Duration on ECMO

- Transfusion volume
- Free cell haemoglobins
- NGAL concentrations
- Serum troponin levels
- Inflammatory cytokines

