4.5 Subgroup analysis

Exploratory analysis may be carried out to assess the relationship of cellular activation with the targeted subgroups:

- Patients on ECMO within 7 days vs 7+ days
- Patients with and without AKI

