Appendix List of variables for reporting

Type	Variable	Unit/Reference	Time points
Demographic, Characteristics at birth	Gestational age	week	
	Preterm	Y/N	
	Gender	M/F	
	Ethnicity	Caucasian /Other	
	Weight at birth	kg	
	Weight	kg	
	APGAR score at birth	0 - 10	
Clinical characteristics			
Heart Rhythm	Sinus Rhythm	Sinus rhythm/AF /Heart block /Paced/Other	
Diagnosis	Diagnosis	Idiopathic PHN /MAS/CDH/ pneumonia/RDS/PH/others	
Cardiac function	LV function	mild / moderate / severe impairment	
	RV function	mild / moderate / severe impairment	
	Shunt	None/Right to left/Left to right /Bidirectional	
	Shunt function	Restrictive / not restrictive	
Mechanical ventilation	Mechanical ventilation Modality	Y/N	
Cannulation	Haemodynamic instability	Y/N	prior to ECMO
	Blood priming	Y/N	
	Clear priming	Y/N	
ECMO Parameters	MAP	mmHg	Pre-ECMO (MAP only); t=0, 12h, 24h, 48h, 72h after start of ECMO and before discontinuation
	FiO2 on ECMO	%	
	FiO2 on ventilator	%	
	ACT	sec	
	Pump flow	ml/min	
	Sweep gas	ml/min	
	RPM	revolutions/min	
Blood saving	Tranexamic acid	Y/N	
	Cell Saver (autologous)	Y/N	
Arrhythmia	Arrhythmia		Placement, removal ECMO
	Cardioversion	Y/N	
	Defibrillation	Y/N	

Type	Variable	Unit/Reference	Time points
Blood gas	pH		Pre-ECMP (PH, Lactate, PCO ₂ , HCO ₃); t=0, 12h, 24h, 48h, 72h after start of ECMO and before discontinuation
	pO ₂	kPa	
	pCO ₂	kPa	
	SaO ₂	%	
	Hb	g/L	
	Glu	mmol/L	
	Lactate	mmol/L	
	HCO ₃	mmol/L	
	Hct	%	
	Na	mmol/L	
	K	mmol/L	
	Ca	mmol/L	
PICU	Lactates	mmol/L	t=0, 12, 24, 48 and 72 hrs post PICU admission & 24hrs after ECMO stop
	PaO ₂ /FiO ₂		
	Total bilirubin	umol/L	
	Fibrinogen	g/L	
	Urea	mmol/L	
	PIM2 score	Total Criteria Point Count	
PMODS score	Total Criteria Point Count	PICU admission & 24h after ECMO stop	
Medication	Inotrope Score	Total Criteria Point Count	
	Vasoactive-Inotrope score	Total Criteria Point Count	
Laboratory test			
Platelets, leukocyte activation	CD41, PAC-1, CD62P, CD64, CD163, CD14, CD16, CD41		t=12h, 24h, 48h, 72h ECMO, and 24h post ECMO and discharge
Granulocyte	CD11b		
Endothelial	ICAM, E-selectin		
Cytokines	IL-6, IL-8, TNF α , MCP-1, MIP-1		
Iron	Total iron, non-transferrin-bound iron		
Free Hb	Free cell Haemogloblins		
Routine lab tests	Creatinine	umol/L	Pre-ECMO, t=12h, 24h, 48h, 72h ECMO, and 24h post ECMO and discharge
	Adjusted Calcium	mmol/L	
	Alkaline Phosphatase	iu/L	
	ALT	iu/L	
	Total Bilirubin	umol/L	
	Amylase	iu/L	
	CRP	mg/L	
	Haemoglobin	g/L	
	Haematocrit	L/L	
	Platelet count	x10 ⁹ /L	
	INR		

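### The fifth time point of the primary markers holds both off-circuit samples (weaned infants) and on-circuit samples (death or treatment withdrawal); nothing in SAP 4.3–4.5 separates them, and the Appendix lists different time points

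*SAP*

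**What the plan says.** **Definition.** SAP 2.1 measures the primary markers at 12, 24, 48 and 72 hours and then "at weaning (24 hours after decannulation) or immediately prior to ECMO support being stopped in case of death or treatment withdrawal". The schedule in SAP 1.5 gives both alternatives one column, headed "24h after decannulation/ prior to ECMO stop for death or withdrawal (+/- 12 hrs". Protocol 5.3.1, 6.1 and 6.8 carry the same either/or rule, and protocol 6.1 counts five blood samples per patient.

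**Analysis.** SAP 4.3 summarises the outcomes as Section 2 defines them: "For continuous variables, mean and standard deviation or median with lower and upper quartiles, as appropriate, will be presented". SAP 4.4 adds "Mixed effects model with patient as random effect will be used to analyse outcomes measured at multiple time points" and "Linear graphs showing the variation of the mean measurements over time will be displayed". SAP 4.5 allows optional exploratory comparisons by AKI and by duration, the latter as "Patients on ECMO within 7 days vs 7+ days". SAP 2.3 defines the long-duration group: "Prolonged ECMO defined as patients remained on ECMO at day 7 (duration of ECMO >168 hours".

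**Appendix.** The time-point cell beside the platelet and leukocyte markers reads "t=12h, 24h, 48h, 72h ECMO, and 24h post ECMO and discharge". It appears to apply also to the granulocyte, endothelial, cytokine, iron and free haemoglobin rows. The point below does not depend on that.

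**The concern.** Which sample an infant contributes at visit five is decided by outcome. Successful weaning leads to an off-circuit sample; death on ECMO or treatment withdrawal leads to an on-circuit one. Protocol 5.4.11 says that a failed wean can end in withdrawal of treatment. Protocol 3.3 says that the circuit surface activates leukocytes and platelets, the cells that most of the primary markers describe. The primary hypothesis (SAP 1.1) links circuit damage and inflammation to failure to wean. At this visit those two things coincide, so a combined mean or SD cannot be read as describing either.

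A plain visit factor in the mixed model would not help, because both sample types carry the same visit label. The duration grouping does not help either. An infant who dies on ECMO on day 4 has a duration below 168 hours and falls in the same group as infants weaned by then.

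The Appendix adds a second ambiguity. Taken literally, it would give a fifth-visit summary for infants who came off ECMO only. An analyst following SAP 2.1 and one following the Appendix could report different fifth-visit results. Under objective 3 these summaries may feed the design of the next study, and the protocol's version of that objective names variance explicitly.

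**Working it through.** There is no planned figure to reproduce: SAP 1.3 states that no formal power calculation was done.

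**1. The passages side by side**

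| Source | 12, 24, 48, 72 h | 24 h after decannulation | Just before ECMO stops | Discharge |
|---|---|---|---|---|
| SAP 2.1, SAP 1.5, protocol 6.1 | yes | yes | yes, same slot | no |
| SAP Appendix, marker rows | yes | yes | no | yes |

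SAP 4.3, 4.4 and 4.5 have no term or split for circuit state or weaning. SAP 4.7 covers only values outside the limits of quantification.

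**2. How many final samples might be on circuit**

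Expected count = 24 × f, where f is the on-circuit share. The documents do not give f. As a proxy I use the mortality figures in protocol 3.2.

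- 10–20% overall: 24 × 0.10 = 2.4; 24 × 0.20 = 4.8. The chance of at least one is 1 − 0.90^24 = 0.92 to 1 − 0.80^24 = 0.995.
- By cause, from survival of 94% (MAS), 77% (idiopathic) and 51% (CDH): 24 × 0.06 = 1.4; 24 × 0.23 = 5.5; 24 × 0.49 = 11.8. The end values would apply only if all 24 infants had that one diagnosis.

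The proxy can err either way. It may be too high for three reasons: deaths after decannulation give no pre-stop sample; the full analysis set requires full consent (SAP 3.1); and samples from infants who die before full consent are kept only with permission (protocol 6.4). It may be too low because the protocol gives 10–20% as the lower end of what ECMO achieves, and because treatment withdrawals also produce pre-stop samples.

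**3. Effect of combining the two types**

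Let d be the assumed on/off-circuit gap in within-type SDs, with equal SDs in the two types. The mean shift from the off-circuit mean is f × d. The variance ratio is 1 + f(1 − f)d².

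| d | Shift, f = 0.10 | Shift, f = 0.20 | Variance ratio, f = 0.10 | Variance ratio, f = 0.20 |
|---|---|---|---|---|
| 0.5 | 0.05 | 0.10 | 1.02 | 1.04 |
| 1.0 | 0.10 | 0.20 | 1.09 | 1.16 |
| 1.5 | 0.15 | 0.30 | 1.20 | 1.36 |

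With d = 1 at the cause-specific extremes, the shift is 0.06 (f = 0.06) to 0.49 (f = 0.49), and the variance ratio is 1.06 to 1.25.

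**4. Comparison with sampling error**

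The SE of a mean at n = 24 is 1/√24 = 0.204 SD. In the table, only f = 0.20 with d = 1.5 exceeds it, and f = 0.20 with d = 1.0 about equals it. The 95% CI for an SD under normality is the estimate times √((n − 1)/χ²), which at n = 24 gives 0.777 to 1.403. Squared, that is 0.60 to 1.97 on the variance scale. Every variance ratio above lies inside this range.

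**5. Precision after splitting**

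At 10–20%, the post-decannulation n is 24 × 0.90 = 21.6 to 24 × 0.80 = 19.2, or about 22 to 19. The SD multipliers become 0.77–1.43 at n = 22 and 0.76–1.48 at n = 19, close to those at n = 24. For the pre-stop group they would be 0.60–2.87 at n = 5 and 0.45–31.9 at n = 2, so an SD for that group would carry almost no information.

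**The case against.** The strongest reply is that pooling is inferred from silence. SAP 4.4 names only the patient random effect and lists no fixed effects for the longitudinal model, not even time. The missing circuit term is therefore not evidence of a decision. SAP 2.1 names the two samples separately, the Appendix records whether the infant was weaned, and the SAP Introduction permits analyses beyond those listed. This stands as a limit on wording: a reader might infer that the SAP has chosen to pool, and it does not say so. It does not remove the gap. SAP 4.3 carries the Section 2 definition forward, and one time point with no splitting rule is most naturally summarised as one.

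A second reply is that the effect is small. That largely stands: most of the scenarios above fall below the sampling error, the gap d is assumed, and the analysis is descriptive or exploratory, with no error rate at stake.

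A third is that the Appendix wording may be shorthand. SAP section 2 introduces it as a list of variables, and the same phrase recurs in the routine laboratory rows. A reader might infer that the SAP means to drop the pre-stop samples; the text does not show that. Even read as shorthand, however, the discharge point has no counterpart in SAP 2.1 or protocol 6.1.

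Finally, a summary in weaned infants only is itself conditional on outcome. That is correct, and the remedy is to label it so.

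**Conclusion.** The point holds as a gap in the analysis plan. One of the five primary-outcome visits holds two kinds of sample whose type is tied to weaning outcome. SAP 4.3 to 4.5 do not separate them, and the Appendix disagrees with SAP 2.1 on the time points. On the natural reading, circuit state and failure to wean are confounded in the fifth-visit mean, SD and graph point.

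The size cannot be established from the documents. The number of on-circuit final samples depends on case mix and on mortality as a proxy, and the on/off-circuit difference is an assumption throughout. The textual finding is firm; the impact is uncertain.

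A reader might conclude that the primary results would be materially distorted. The documents do not support that: they give no marker values from which a difference could be derived, four of the five visits are unaffected by the shared slot, and the effect may be smaller than the sampling error at n = 24. Nor is there anything wrong with collecting both samples; only their analysis needs specifying. This is a minor, inexpensive clarification.

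**What to change.** 1. **Summaries and graphs (SAP 4.3, 4.4).** Report the fifth visit by sample type, using the weaned yes/no variable already in the Appendix. Give the post-decannulation mean and SD for weaned infants, labelled as conditional on weaning. List the pre-stop samples individually, with no SD and no test.
2. **Mixed model (SAP 4.4).** Keep both types, coded as two separate levels of the visit factor. State that any contrast between on-circuit and off-circuit levels is descriptive, because being off circuit coincides with having been weaned.
3. **Classification.** Assign every sample to on or off circuit by its actual collection time against the decannulation time, not by its scheduled hour against total ECMO hours. With windows of ±12 hours the scheduled hour can mislead. If ECMO lasted 70 hours, a 72-hour sample drawn at 65 hours is on circuit; if it lasted 75 hours, one drawn at 80 hours is off circuit. Collection times should exist: protocol 7.2 says samples are identified by the time they were taken, and the timing-deviation rule in protocol 6.10 cannot be applied without them. Protocol 6.10 also records dates and times of relevant outcomes.
4. **Appendix.** Make the marker time points agree with SAP 2.1: add the pre-stop sample, and remove or explain discharge.

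**Cost.** SAP wording, a split display, one extra model parameter, and a slightly smaller n for the post-decannulation summary (about 19 to 22 at 10–20% mortality, fewer if the case mix is more severe). No new samples are needed.
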